### Measurement methods and variables

- **Assessment of exercise capacity with cycle ergometry.** Cycle-ergometry will be performed in progressive steps of one minute up to its maximum. We will use a state-of-the-art Vyntus CPX ergospirometer from the firm Jaeger-CareFusion. Maximum oxygen consumption, aerobic-anaerobic thresholds, respiratory compensation point, ventilatory limitation study, calorimetry, forced spirometry F/V, slow spirometry + MVV, maximum voluntary ventilation, cardiac output and physiological dead space will be assessed. The subsequent evaluation of the data will be carried out through the Sentry program platform
- **6-minute walk test (6MWT):** it is carried out in an absolutely flat corridor with a length equal to or greater than 30m, placing cones to mark the ends of the route. The distance traveled in a period of 6 minutes will be

calculated according to the recommendations of the American Thoracic Society (ATS)

- **Physical activity level** using the Multisensor ArmBand accelerometer. (SenseWear mini armband; BodyMedia,) as referenced in the study by [name] et al ([name] 2016). It is placed on the right triceps and provides information on calorie consumption and physical activity levels, which are subsequently, analyzed using specific software (INNERVIEW professional version 8, BodyMedia, Pittsburgh, PA). ↗ Quality of life in Saint George respiratory questionnaire (Soto Campos 2009). 50 items divided into three scales: symptoms, activity and impact. Symptom scale items refer to frequency and severity of respiratory symptoms
- **Cough Severity Questionnaire with LCQ** (Murray et al. 2009)(Annemarie L. Lee et al. 2017). The LCQ measures the physical, psychological, and social impact of chronic cough. It consists of 19 items. Validated in BQ not CF.
- **Severity and prognosis by E-FACED:** number of exacerbations in the previous year; F: percentage of predicted FEV1; A: age; C: chronic colonization by *Pseudomonas aeruginosa*; E: Extension [number of lung lobes affected by bronchiectasis]; D: dyspnea) have been proposed to stratify BE patients according to their main dimensions (symptoms, lung function, imaging, and microbiology). 0-3 points: mild bronchiectasis. 4-6 points: moderate bronchiectasis. 7-9 points: severe bronchiectasis
- **Pulmonary function test:** measurements through a Jaeger Viasys Mastercope spirometer. Forced expiratory volume in 1 s (FEV1), Forced vital capacity (FVC).
- **Other variables:** demographic (sex, age, weight, height, body mass index), comorbidities (hypertension, diabetes, dyslipidemia), smoking (packs/year): Modified dyspnea scale. Medical Research Council (MRC).
- Other variables: demographic (Sex, age, weight, height, body mass index), comorbidities (HBP, Diabetes, Dyslipidemia), Smoking (packs/year): Modified dyspnea scale. Medical Research Council (MRC).

## Statistical analysis

For the calculation of the sample size, a power of 95% is used, a hypothetical loss rate during the study of 15%, a total of 30 patients per group would be included, enough to demonstrate our hypothesis and find statistically significant differences in the capacity of exercise and the change in physical activity in the two populations.

Statistical analysis was performed using the statistical analysis software IBM SPSS Statistics (SPSS v23, Chicago, IL, USA). For quantitative variables, the values are expressed as mean +/- standard deviation, while in the case of qualitative variables; their values are included as frequency and percentage. The comparison between groups was carried out using the T test for independent samples in the event that the data behaved according to a normal distribution. Otherwise, the Mann-Whitney U test was used for independent samples. The comparison of the effects of respiratory rehabilitation was performed with the Student's t test for related samples when the data follow a normal distribution and the Wilcoxon signed rank test for related samples. In all cases, the minimum level of significance was considered to be  $p < 0.05$ . If statistically significant differences are identified between the different groups studied, "a posteriori" comparison tests will be carried out, such as the Mann-Whitney U test according to application criteria, with the level of significance corrected.

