### Exclusion criteria

- Smokers or former smokers of less than 6 months or with a history of consumption of 15 packs/year.
  - Cystic fibrosis.
  - Active infections (bronchopulmonary aspergillosis, pulmonary tuberculosis).
  - Active tuberculosis.
  - poorly controlled asthma

- Chronic obstructive pulmonary disease.
- Diseases that prevent adequate performance of exercise (neuromuscular pathology or residual injuries)
- Medical diseases that put the individual at risk of a decompensation due to the performance of any physical activity or cardiopulmonary stress test (unstable ischemic heart disease, acute myocardial infarction less than 1 month).
- Pregnancy.
- Mental disorder that prevents the adequate interpretation of the indications or performance of the tests.

- **Study design.**

Prospective and randomized study with consecutive inclusion of patients from the Non-CF bronchiectasis BE monographic clinic of the Virgen Macarena Hospital (Seville). Patients who meet the inclusion criteria will be randomized into two groups: control and intervention, patients will be assigned to each group using a numerical sequence generated by computer until the sample size is obtained.

The control group will receive basic recommendations on physical activity and the intervention group will be included in a mixed respiratory rehabilitation program (combining home and hospital sessions).

**Visit 1:** inclusion of patients with BE who comply with inclusion. Signature of informed consent and randomization of patients.

**Visit 2:** All patients will undergo an initial assessment of the degree of physical activity by means of accelerometers (®Sensewear arm band) for 3 days including weekends, as well as pulmonary function and exercise tolerance tests, stratification of severity according to the E-FACED scales.

\* Control group: written recommendations on performing some physical activity for at least 30 minutes of moderate intensity according to the recommendations of the Spanish Society of Pulmonology and the Andalusian Society of Pulmonology and Thoracic Surgery. (Casilda Olveira, Costa, and Martínez-García 2016) , (C Olveira et al. 2010). A phone call every 15 days to assess the physical activity carried out without talking about exercise or physical activity.

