\* Intervention group: Patients will be included in an 8-week outpatient program with recall sessions led by our physiotherapist once every 2 weeks in the hospital's Respiratory Rehabilitation gym. In the first session, patients will be instructed on how to perform home exercises as well as how to use the Borg scale. A phone call weekly to provide support and general advice about exercise or physical activity.

The program will combine isotonic strength and resistance exercises. Resistance training will consist of bicycle or walking exercises (depending on the availability of each patient), with a progressive increase in distance or time of completion depending on symptom control.

The strength training program will include upper and lower limb exercises that will begin with no load and to which weights will be progressively added depending on the control of symptoms, in 2 sets of 6-8 repetitions:

- Hanger (to work the latissimus dorsi muscle).
- Butterfly (pectoralis major muscle work).
- Neck press (brachial triceps and deltoid work).
- Flexion of legs (work of biceps femoris and gastrocnemius).
- Extension of legs (work of quadriceps femoris): place a weight or ballast. Stretch the leg and raise the thigh
- Exercises with elastic bands: upper and lower limbs. Separate both ends of the tape as much as possible.
- Walking: increase the walking time progressively.
- Bicycle or treadmill: submaximal exercise. Constant pedaling at about 60 rpm with moderate intensity.

Patients will be encouraged to maintain the exercises after the study.

**Visits 3, 4 and 5:** at 8 weeks (time of completion of the rehabilitation programs), 6 months and 12 months, respectively. At the end-of-program and follow-up visits, all the measurements made at the baseline visit will be repeated, as well as the record of exacerbations.

All patients will receive an educational program about their disease as well as an individualized respiratory physiotherapy program including relaxation techniques, secretion management and assessment of nutritional status.

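### The between-arm comparison uses no baseline adjustment and no stated scale: the test is valid, but it gives up precision that measurements already planned could supply.

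*Combined protocol and SAP*

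**What the plan says.** The Statistical analysis section is the whole statistical plan. For the arms it says "The comparison between groups was carried out using the T test for independent samples" when the data are normal. For other data it says "Otherwise, the Mann-Whitney U test was used for independent samples". Baseline enters only through a within-patient test: "The comparison of the effects of respiratory rehabilitation was performed with the Student's t test for related samples", with Wilcoxon signed rank as the alternative. No analysis of covariance, regression, mixed model or covariate is named in any section.

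The scale of the between-arm comparison is not given. The sample-size sentence mixes two scales, expecting to "find statistically significant differences in the capacity of exercise and the change in physical activity in the two populations".

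Under Study design, Visit 2 covers accelerometry "as well as pulmonary function and exercise tolerance tests, stratification of severity according to the E-FACED scales". At 8 weeks, 6 months and 12 months "all the measurements made at the baseline visit will be repeated, as well as the record of exacerbations". Allocation follows a computer-generated sequence, with no stratification or balancing described. Randomisation takes place at Visit 1, before the Visit 2 baseline tests.

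**The concern.** The comparison that uses the randomisation is the between-arm one, and it makes no declared use of the baseline values the trial collects. With 30 patients per arm, fewer after losses, precision is scarce. For measures such as exercise capacity, a patient's baseline value usually predicts part of the follow-up value. An analysis that ignores it leaves that predictable part in the error term.

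The silence on scale adds a second problem. A t test on follow-up values and a t test on changes have different precision, and which is better depends on the correlation. Because the choice between t and Mann-Whitney also depends on the data, the main analysis is not fixed until results are in hand.

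**Working it through.** **The plan's own figure.** The Statistical analysis section gives 30 per group, 95% power and 15% loss, but no effect size or SD, so 30 cannot be reproduced. It can only be inverted. With two-sided 5% (sidedness is not stated) and 95% power, n per arm = 2(1.96 + 1.645)²/d² = 25.99/d², where d is the difference in SD units.
- d = 1.0 gives 26 per arm, and 26/0.85 = 30.6, so 31.
- d = 1.02 gives 25 per arm, and 25/0.85 = 29.4, so 30.

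The stated size therefore fits a difference of about 1 SD. This is an inference, not something the plan says.

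**Inputs for the comparison.**
- From the plan: 30 × 0.85 = 25.5 evaluable per arm, taken as 25.
- Assumed: equal SDs at baseline and follow-up; correlation r between them; illustrative effects of 0.5 SD and 1 SD.

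**Variance of the between-arm estimate**, with the follow-up-value t test set to 1:
- change scores: 2(1 − r)
- baseline-adjusted model: 1 − r²
- saving of adjustment against follow-up values: r²
- saving against change scores: 1 − (1 − r²)/[2(1 − r)] = (1 − r)/2

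| r | Change scores | Adjusted | Saving vs follow-up | Saving vs change |
|---|---|---|---|---|
| 0.3 | 1.40 | 0.91 | 9% | 35% |
| 0.5 | 1.00 | 0.75 | 25% | 25% |
| 0.6 | 0.80 | 0.64 | 36% | 20% |
| 0.7 | 0.60 | 0.51 | 49% | 15% |
| 0.8 | 0.40 | 0.36 | 64% | 10% |

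Below r = 0.5 change scores are less precise than follow-up values; above it they are more precise. Adjustment is at least as good as either throughout. A 20,000-run simulation at 26 per arm gave adjusted-to-follow-up variance ratios of 0.64 (r = 0.6) and 0.37 (r = 0.8), and adjusted-to-change ratios of 0.83 and 0.92. These are close to the formulas.

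**Power at 25 per arm, 0.5 SD, two-sided 5% (noncentral t):**

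| r | Follow-up | Change | Adjusted |
|---|---|---|---|
| 0.3 | 41% | 31% | 44% |
| 0.5 | 41% | 41% | 52% |
| 0.6 | 41% | 49% | 58% |
| 0.7 | 41% | 61% | 68% |
| 0.8 | 41% | 78% | 82% |

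The 95% CI half-width on follow-up values is 0.57 SD. Adjusted, it is 0.46, 0.41 and 0.34 SD at r = 0.6, 0.7 and 0.8.

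**At 1 SD**, unadjusted power on follow-up values is about 93%, and adjustment at r = 0.6 raises it to about 99%.

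**Chance imbalance.** The baseline difference between arms has SD √(2/n): 0.26 at n = 30 and 0.28 at n = 25, in SD units. A difference of 0.3 SD or more occurs in 25% and 29% of randomisations respectively. A follow-up-value analysis carries r times that difference into the estimate.

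**Order of visits.** Suppose knowing the arm shifted baseline performance by 0.2 SD (an assumption). The adjusted estimate would then be displaced by r × 0.2 = 0.12 to 0.16 SD at r of 0.6 to 0.8. A change-score estimate would be displaced by the full 0.2 SD. A follow-up-value test would not be affected.

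**The case against.** The strongest reply is that nothing here is wrong in the inferential sense. Under randomisation the two-sample test is unbiased with valid type I error, and its interval already allows for chance imbalance. That stands. A reader might infer that the planned test is biased or invalid, or that imbalance is a harm additional to lost precision. Neither is supported: they are one issue seen conditionally and on average.

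A reader might also infer that the plan forgoes a third to two thirds of the variance. That needs r of about 0.58 to 0.82 and a test on follow-up values, and the documents state neither. The objectives speak of changes after rehabilitation, and the sample-size sentence refers to change in physical activity. Over the same range of r, the saving against change scores is only about 21% to 9%.

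The 0.5 SD effect is illustrative. At the roughly 1 SD that the stated sample size implies, little power remains to be gained, although the interval would still narrow.

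Nor can it be said that every outcome has a baseline. Visit 2 does not name the St George or Leicester Cough questionnaires, exacerbations are recorded at follow-up, and no instrument is given for anxiety or depression.

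Finally, adjustment brings its own condition, a baseline unaffected by knowledge of the arm, and the present visit order does not secure it. That stands and belongs in the fix.

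What the reply does not remove is that adjustment is more precise than either unadjusted scale at every r tabulated, and that the plan leaves the scale open.

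**Conclusion.** The point holds as a matter of efficiency and prespecification. The plan has only unadjusted between-arm tests on an unstated scale, while exercise tolerance, physical activity and lung function all have a baseline value. Over r from 0.3 to 0.8, adjustment saves 9% to 64% of the variance against follow-up values, or 35% to 10% against change scores. At 0.5 SD with 25 per arm and r of 0.6 to 0.8, the gain in power is 17 to 41 points over follow-up values (58 − 41 and 82 − 41), but only 4 to 9 points over change scores (82 − 78 and 58 − 49). At 1 SD the gain is small.

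The absence of adjustment and of a stated scale can be read directly from the text. The size of the gain rests on r, the effect size and equal SDs, all of which are assumed. This is an improvement the sponsor should make, not a flaw that would invalidate the result.

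**What to change.** For each continuous outcome with a baseline measurement, replace the independent t / Mann-Whitney rule with a linear model of the follow-up value on arm and the baseline value of the same variable. Fit it at 8 weeks, 6 months and 12 months, and report the adjusted mean difference with its 95% CI. This also settles the choice between follow-up values and changes. In a 3,000-trial simulation the adjusted test kept its type I error at 0.04–0.05, and at 0.049 with lognormal skew, so moderate non-normality is not in itself a reason to go back to a rank test. Adding E-FACED as a further covariate is optional: no gain has been calculated for it, and it overlaps with baseline function through FEV1 and dyspnoea.

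The analysis costs one sentence and one degree of freedom, with the same patients and the SPSS version already named. The larger cost is procedural. Complete the Visit 2 baseline tests before allocation is disclosed, which means changing the order of the visits or withholding the allocation until testing is done. If that is not feasible, state that baseline was measured after randomisation as a limitation of the adjusted analysis.

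### The observed distribution chooses between the t test and Mann-Whitney, the choice is not fixed per outcome or visit, and no between-arm effect with a confidence interval is planned

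*Combined protocol and SAP*

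**What the plan says.** All of the analysis wording is in the Statistical analysis section.

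- **Between-arm test.** The arms are compared "using the T test for independent samples in the event that the data behaved according to a normal distribution". For data that fail this condition, the plan turns to ranks: "Otherwise, the Mann-Whitney U test was used for independent samples". No normality test or threshold is named. The section does not say whether the check is made per outcome, per arm or per visit.
- **Within-group test.** The comparison of rehabilitation effects "was performed with the Student's t test for related samples when the data follow a normal distribution and the Wilcoxon signed rank test", so the same data-driven choice applies there.
- **Reporting.** "For quantitative variables, the values are expressed as mean +/- standard deviation", whichever test was used, with significance at p < 0.05. No between-arm difference, effect size or confidence interval is mentioned anywhere in the document.
- **Post hoc step.** "If statistically significant differences are identified between the different groups studied", further "comparison tests will be carried out, such as the Mann-Whitney U test according to application criteria, with the level of significance corrected". The correction is not named.

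Two other places bear on this. The Study design text (printed under the Exclusion criteria heading) has patients "randomized into two groups: control and intervention". The visit schedule repeats all baseline measurements at 8 weeks, 6 months and 12 months.

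**The concern.** The t test addresses a difference in means. Mann-Whitney addresses whether values in one arm tend to exceed those in the other. If the sample decides between them, the quantity tested is unknown until the data are seen. Nothing in the plan prevents the same outcome from being tested one way at 8 weeks and the other way at 12 months. A change in significance between those visits could then reflect a change of test as well as a change in benefit, and durability is what the later visits are there to show. A Mann-Whitney p-value printed beside means and SDs also describes something other than what was tested.

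The larger gap is the estimate. With about 25 completers per arm in a study titled as a pilot, the useful product is the size of the between-arm effect and its uncertainty. As written, the plan commits to neither.

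**Working it through.** **Inputs from the plan.** Two arms; 30 per group; 15% loss; significance at 0.05 (two-sided assumed, as sidedness is not stated); three post-baseline visits. Completers per arm: 30 × (1 − 0.15) = 25.5, taken as 25. The plan gives no effect size or SD, so its 30 per group cannot be reproduced and no stated figure is available to check here.

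**Assumptions, not in the plan.** The normality check is Shapiro-Wilk at 5% in each arm. Data are normal or lognormal (sigma 0.3 mild, 0.5 stronger skew), with a shift of 0.5 SD. The correlation between visits, and between baseline and follow-up, is 0.7. Simulations used 2,000 to 10,000 trials per setting; ranges below span separate runs.

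**Step 1: how often the gate selects Mann-Whitney at one visit.** About 10% with normal data, 51%-52% with sigma 0.3 and 86%-87% with sigma 0.5.

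**Step 2: whether three visits get the same test, if the check is repeated at each visit.** They do not all get the same test in about 25% of trials with exactly normal data, and in 64%-65% with sigma 0.3.

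**Step 3: how often the gate changes the verdict at 0.5 SD.** The event that matters is that the gate selects Mann-Whitney and its verdict at 0.05 differs from that of the t test.

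| Data | Gate changes verdict | Power, t test alone | Power, gated rule |
|---|---|---|---|
| Normal | 0.8%-1.0% | about 41% | about 41% |
| Lognormal, sigma 0.3 | 6.5%-6.9% | about 42% | about 46% |
| Lognormal, sigma 0.5 | 15%-16% | 43%-45% | 55%-56% |

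**Step 4: type I error of the gated rule.** Between 4.6% and 5.8% across settings and runs, so close to nominal.

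**Step 5: the interval the plan does not ask for.**
- Unadjusted half-width: t(0.975, 48) × √(2/25) = 2.011 × 0.283 = 0.57 SD.
- Baseline-adjusted at correlation 0.7: 0.569 × √(1 − 0.49) = 0.569 × 0.714 = 0.41 SD.

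**Step 6: power of the baseline-adjusted difference at 0.5 SD.** The effective standardised effect is 0.5 / 0.714 = 0.70. With 25 per arm, the noncentral t gives about 68%. Simulation gives about 67% for normal data and for both lognormal settings, with type I error about 5%. The gated rule has 41% to about 55%.

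**Step 7: what the fix can cost.** Without useful baseline information, the mean-based test under sigma 0.5 has 42.8% power against 55.9% for the gated rule in the least favourable run: 55.9 − 42.8 = 13.1 points.

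**The case against.** The strongest defence is that gating between t and Mann-Whitney is common practice and does little harm here. Type I error is near nominal, and under skew the gate gains power over the t test alone. Both statements stand. A reader might infer that choosing the test from the data inflates false positives; the calculations do not support that.

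Several other inferences are tempting but go beyond the documents:

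- **The rate at which the two tests disagree as the harm.** If both tests are run on the same data at 0.5 SD, they disagree in about 7%-8% (normal) to 16% (sigma 0.5) of trials. The plan runs one test per comparison, so Step 3 is the relevant count. With normal data it is about 1%.
- **Switching between visits as fact.** The plan does not say the check is repeated at each visit or in each arm. One choice per variable fits the wording equally well. The documented defect is that the choice is left open; the 25% and 64%-65% figures hold only under the per-arm, per-visit reading.
- **The post hoc step as a second Mann-Whitney on the same two arms.** This is one reading. The plan defines three E-FACED severity classes, and its title and its section on practical applicability raise the relation of severity to exercise capacity. Corrected pairwise tests would be natural there. However, the Statistical analysis section specifies no comparison across those classes, so the scope is unresolved. The level is to be corrected, "such as the Mann-Whitney U test according to application criteria, with the level of significance corrected", and a step triggered only by significance cannot create a new positive.
- **A null result as uninterpretable.** Arm means, SDs and group sizes let a reader derive an unadjusted difference and interval. That interval would not match a Mann-Whitney p-value or use the baseline values, but the phrase is too strong.
- **The listed reference on a minimal important difference.** Not using a bibliography entry is not an analysis error. By its title it concerns field walking tests, whereas the primary objective uses a cardiopulmonary test.

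**Conclusion.** The concern holds in limited form. The plan lets the observed distribution choose the between-arm test, does not fix that choice per outcome or visit, and commits only to arm-wise mean and SD with a p-value. No between-arm effect with a confidence interval is planned.

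The effect of the gate on conclusions ranges from negligible with normal data to material with marked skew, and it does not come through false positives. The more useful gain is from replacing the rule with a baseline-adjusted estimate: at 0.5 SD and a baseline correlation of 0.7, the interval is about 29% narrower (1 − 0.714) and power is some 12 to 26 points higher (67 − 55; 67 − 41).

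These sizes rest on the assumed Shapiro-Wilk gate, distributions, effect and correlation, none of which the plan gives. The text-based finding, an unfixed test and no planned estimate, needs none of them.

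**What to change.** In the Statistical analysis section:

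1. For each continuous outcome, pre-specify one between-arm mean difference adjusted for the baseline value, with a 95% CI, in the same form at 8 weeks, 6 months and 12 months. Drop the normality gate for this comparison.
2. Name a bootstrap or permutation version as a sensitivity analysis.
3. Describe skewed variables by median and quartiles in the tables.
4. Remove the post hoc step for the two-arm comparison, or state that it applies only to comparisons among more than two groups, such as E-FACED classes, and name the correction.

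The cost is wording only, since baseline values are already collected and all measurements are repeated at follow-up. The downside is the possible loss in Step 7, up to about 13 points of power when skew is strong and the baseline correlation weak. If an outcome is expected to behave that way, a transformation or a rank-based estimate with its interval can be fixed for it in advance, before any outcome data are seen.

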## **Relationship between the Severity of Bronchiectasis and Exercise Capacity after a Pilot Program for Home Respiratory Rehabilitation at the Virgen Macarena University Hospital**

### **BACKGROUND AND CURRENT STATE OF THE SUBJECT**

Bronchiectasis not associated with cystic fibrosis (non CF bronchiectasis) is bronchial dilatations characterized by inadequate mucociliary clearance, whose main clinical expression is cough with purulent expectoration and dyspnea, leading to exercise limitation. In order to try to quantify the severity of the disease and its prognosis, in recent years different scales have been developed that take into account clinical, radiological and functional parameters (FACED and BSI).

The objective of the treatment of the disease lies in the prevention of exacerbations, reduction of symptoms, improvement in quality of life and stabilization of lung function (Polverino et al. 2017). Based on these objectives, we have tried to develop tools, until now not available in all media, such as the development of specific respiratory rehabilitation programs (PRR). Although the long-term benefits of PPRR have not been objectified or demonstrated, there is a common consensus on the need to include this type of intervention in the management of patients with bronchiectasis (strong level of recommendation) (Polverino et al. 2017), since they could stabilize lung function and exercise capacity, as well as influence exacerbations, although more studies are still needed in this regard. On the other hand, it is also not very clear where and when to carry out this type of program, and there is a need to implement and optimize respiratory rehabilitation programs in non-traditional settings, at home or in an exacerbation (Rochester et al. 2015) (Wedzicha et al. 2017)(Pasteur et al. 2010).

Most of the studies carried out in relation to RR and non-CF bronchiectasis have focused on outcomes on quality of life and lung function with disparate results (Annemarie L Lee et al. 2014), however there are fewer data in relation home base rehabilitation program . To date, there are several clinical trials that analyze exercise capacity and tolerance in patients with bronchiectasis undergoing RP, with a clear improvement in these parameters after completion (Murray, Pentland, and Hill 2009)(Zanini et al. 2015)(Singh et al. 2014)(J. Bradley, Moran, and Greenstone 2002).

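### The effect of rehabilitation is assigned to before/after tests within an arm, not to the randomised comparison with control

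*Combined protocol and SAP*

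**What the plan says.** The Study design part of the Method section sets up a randomised parallel-group trial: "Patients who meet the inclusion criteria will be randomized into two groups: control and intervention". Measurements are taken at baseline and repeated at 8 weeks, 6 months and 12 months.

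The Statistical analysis section then allots tests by purpose:

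- For arms against each other: "The comparison between groups was carried out using the T test for independent samples", or Mann-Whitney U if the data are not normal. No outcome, visit or change score is attached.
- For the effect of the programme: "The comparison of the effects of respiratory rehabilitation was performed with the Student's t test for related samples", or "the Wilcoxon signed rank test for related samples".

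The sample-size sentence in the same section says that the trial should "find statistically significant differences in the capacity of exercise and the change in physical activity in the two populations". The primary objective speaks of effects and changes after the programme and states no contrast with control.

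Two features of the design bear on how a within-arm change can be read. Controls are given "written recommendations on performing some physical activity for at least 30 minutes of moderate intensity". In addition, "All patients will receive an educational program about their disease as well as an individualized respiratory physiotherapy program".

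**The concern.** A related-samples test in an unmatched parallel-group trial can only be a before/after comparison within patients. It shows whether an arm changed, not whether rehabilitation changed it more than control did. The one sentence that names the rehabilitation effect therefore leaves out the comparison that randomisation was meant to provide.

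The weakness matters here because both arms receive active care. Education and individualised physiotherapy go to everyone, and controls also receive written activity advice, although their fortnightly calls are meant to avoid the subject of exercise. Some improvement in both arms is plausible, and a paired test in the intervention arm cannot separate it from the effect of the programme.

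The paired test can also fail in the other direction. The Background section recommends programmes partly "since they could stabilize lung function and exercise capacity". If the benefit is that the intervention arm holds steady while controls decline, a before/after test in the intervention arm is null although the benefit is real.

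**Working it through.** **Inputs from the plan.** 30 patients per group, 15% loss, 95% power, significance level 0.05 (Statistical analysis section). Sidedness is not stated; two-sided is assumed. Completers per arm: 30 × 0.85 = 25.5, taken as 25.

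**The plan's own figure.** The 30 per group cannot be reproduced, because no effect size or SD is given. Solving backwards with the normal approximation, 25 per arm gives 95% power for a standardised between-arm difference of √(2/25) × (1.960 + 1.645) = 1.02. The exact t calculation gives 1.04. A paired test in 25 patients has 95% power for a change of (1.960 + 1.645)/√25 = 0.72 SD of the change. The plan does not say which test the 30 per group was sized for.

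**Case 1: both arms change equally, with no true effect.** Let δ be the shared change in SDs of the change. The paired t test has 24 df, critical value 2.064 and non-centrality δ√25 = 5δ. The assumed values of δ are not from the documents. The arms are taken as independent and the data as normal.

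| δ | Non-centrality | Intervention-arm paired test significant | Intervention significant, control not | Between-arm t test on change significant |
|---|---|---|---|---|
| 0.2 | 1.0 | 16% | 13% | 5% |
| 0.3 | 1.5 | 30% | 21% | 5% |
| 0.4 | 2.0 | 48% | 25% | 5% |
| 0.5 | 2.5 | 67% | 22% | 5% |

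The fourth column is p(1 − p), where p is the third. For example, at δ = 0.4 it is 0.484 × 0.516 = 0.25. Running the paired test in both arms and contrasting the two p-values is therefore no remedy. A simulation of 200,000 trials per case agrees: 0.158, 0.303, 0.484 and 0.669 for the paired test, and 0.049 to 0.051 for the between-arm test.

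**Case 2: the intervention arm is stable and controls decline.** The paired test in the intervention arm shows improvement in 2.5% of trials, which is the upper tail of a two-sided 5% test. The between-arm test on change has 48 df and non-centrality δ√(25/2), where δ is now the control decline:

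- Controls fall 0.5 SD: non-centrality 1.77, power 41%.
- Controls fall 0.8 SD: non-centrality 2.83, power 79%.

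**What baseline adjustment adds.** The between-arm difference detectable at 95% power with 25 per arm is 1.04 SD on follow-up values. Multiply by √(2(1 − r)) for change scores and by √(1 − r²) for ANCOVA, where r is the assumed correlation between baseline and follow-up.

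| r | Follow-up values | Change scores | ANCOVA |
|---|---|---|---|
| 0.5 | 1.04 | 1.04 | 0.90 |
| 0.7 | 1.04 | 0.81 | 0.74 |
| 0.8 | 1.04 | 0.66 | 0.62 |

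The plan does not say whether exercise capacity is compared on follow-up values or on changes, so its sensitivity depends on a choice not yet made.

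**The case against.** The strongest reply is that the right kind of test is already in the plan. The independent-samples test is listed before the paired ones, the sample-size sentence aims at a difference between two populations, and the last sentence of the section plans further tests if the groups differ. Since the primary objective speaks of effects and changes after the programme, the sentence on effects could simply mean before/after change, reported alongside a comparison of the arms. On that reading the fault is a loose label, and the error rates above apply only if the authors set aside a test that they listed.

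Much of this is true. A between-arm aim exists, and the harm depends on how the paired result is used. It does not settle the matter. The listed between-arm test has no outcome or visit attached and could as well be a comparison of baseline characteristics. The primary objective states no contrast with control either. Someone following the text could report a significant paired test as efficacy whatever the between-arm result.

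Three smaller points are fair. The shared changes are assumptions and show how the error behaves, not how likely it is in this trial. The stabilisation case is only illustrative: the documents mainly expect improvement, and a decline of 0.5 or 0.8 SD in controls by 8 weeks has no source in them. The gain from ANCOVA over change scores depends on r and is small at r = 0.8, so it is a reason to prefer one between-arm analysis over another and not part of the defect.

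**Conclusion.** The concern holds: the section is wrong as written and must be fixed. The plan gives the rehabilitation effect to tests that ignore the control arm, and nothing elsewhere makes the between-arm comparison the test of efficacy.

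If the paired test carries the claim, the chance of a false efficacy finding is 16% to 67% instead of 5%, for an assumed shared change of 0.2 to 0.5 SD. This rests on 25 completers per arm, two-sided 0.05, normal data and no true arm difference. The direction of the error does not depend on those sizes, since any change common to both arms raises the rate above 5%. The paired tests remain valid as descriptions of change within an arm.

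**What to change.** Replace the sentence on the effects of rehabilitation with wording such as:

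> The effect of rehabilitation is the between-arm difference in exercise capacity on the cardiopulmonary test (one named variable, for example maximum oxygen consumption) at 8 weeks, with patients analysed in the arm to which they were randomised. It is estimated by ANCOVA of the 8-week value on arm and baseline value and reported with a 95% confidence interval. Paired tests within each arm are descriptive and support no efficacy claim.

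An alternative is one linear mixed model over 8 weeks, 6 months and 12 months, with arm-by-visit and baseline-by-visit terms, reading the 8-week contrast as primary. Of the two, only the mixed model keeps patients who miss the 8-week visit but attend a later one. The smallest acceptable repair is to apply the independent-samples test already listed to change from baseline at a stated visit, and to label the paired tests descriptive.

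The cost is one or two sentences. Baseline and follow-up values are already collected, SPSS is already the planned software, and no patients or visits are added. Because the section is partly in the past tense, the change should be dated before outcome data are analysed. If analysis has begun, the new contrast should be labelled post hoc.
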